### 6.4 Vital Signs

All vital sign measurements will be taken after the subject is supine for 5 minutes.

Vital signs (including blood pressure and pulse [radial or brachial to be measured over 30 seconds if performed manually]), respiration rate, and body temperature (oral) will be measured at screening. Vital signs will be measured on Day -1, prior to administration of apixaban on the morning of Days 1-4, 30 minutes prior to study drug, at 1.5, 4, 8 and 24 hours post-study drug. Please see below for tolerance window to perform vital sign assessments:

Vital Signs Tolerance Window

Vital Sign Time Point	Tolerance Window
Pre-dose	-60 minutes to 0 hour
>0 hour - 4 hour	-10 minutes to +10 minutes
>4 hour - 12 hour	-20 minutes to +20 minutes
>12 hour - 24 hour	-30 minutes to +30 minutes
Study Exit/Early Termination	-30 minutes to +30 minutes

Vital signs, respiratory rate, and body temperature will be re-assessed at the discretion of the investigator if warranted by the subject's condition and/or in the following situations:

- Systolic blood pressure less than 90 mmHg or greater than 180 mmHg
- Diastolic blood pressure less than 50 mmHg or greater than 100 mmHg
- Pulse less than 40 beats per minute or greater than 110 beats per minute
- Respiratory rate less than 10 breaths per minute or greater than 30 breaths per minute
- Body temperature less than 36.1°C (97.0°F) or greater than 37.3°C (99.2°F)

An abnormal vital sign that is considered clinically significant by the Investigator will be recorded as an adverse event. Additional vital sign measurements may be conducted at any time throughout the study, if deemed necessary by the Investigator.

## **6.5 Stroke Assessments**

Stroke assessments will be performed by PI or designee at approximately 3 hours post-apixaban dose on the morning ( $\pm 1$ -hour window) on Day 1 to 4. PI or designee will check for stroke warning signs and physical symptoms:

Stroke warning signs:

- Sudden weakness or numbness of the face, arm or leg, especially on one side
- Sudden confusion or difficulty understanding
- Trouble speaking, walking or seeing
- Dizziness or loss of balance
- Sudden onset of severe headache

Physical symptoms:

- Facial smiling or showing of teeth on one side
- One arm does not move or drifts compared to the other on extension
- Abnormal slurred speech, improper choice of words, inability to speak or acute confusion and disorientation

## **6.6 Clinical Laboratory Tests**

Blood and urine samples for safety laboratory tests will be collected at screening, at check-in, and prior to discharge from the clinical site. Safety laboratory tests may also be done at any time during the study at the discretion of the Investigator to monitor AEs. Subjects will be in a seated or supine position during blood collection.

### **6.6.1 Fecal Occult Blood Tests**

Fecal occult blood tests will be done at check-in. Fecal occult blood kits will be given to all subjects at screening to provide stool samples for testing at check-in. In the event occult blood kits are not returned, a rectal exam for stool sample may be performed at the discretion of the Investigator. Occult blood test results must be negative during check-in to continue study participation. Additional fecal occult blood testing may be conducted at any time throughout the study, if deemed necessary by the Investigator.

## 6.6.2 Laboratory Parameters

Values for the clinical laboratory tests listed below will be determined by accredited laboratory facility(ies).

CLINICAL CHEMISTRY	HEMATOLOGY
The following clinical chemistry tests will be performed at screening, check-in, and discharge from the study:	The following hematology tests will be performed at screening, check-in, and discharge from the study:
Alanine aminotransferase (ALT)	Hematocrit
Albumin (ALB)	Hemoglobin
Aspartate aminotransferase (AST)	Platelet count
Blood urea nitrogen (BUN)	RBC
Calcium	WBC / with differential
Chloride	
CO 2	COAGULATION
Creatinine (CR)	The following coagulation tests will be performed at screening, check-in, and discharge from the study:
Direct bilirubin (DBIL)	
Glucose	
Indirect bilirubin (IBIL)	PT-PTT
Lactose dehydrogenase (LDH)	
Magnesium	URINALYSIS
Potassium	The following urinalysis tests will be performed at screening, check-in, and discharge from the study:
Sodium	
Total bilirubin (TBIL)	Appearance
Total Protein	Bilirubin
	Blood
	Color
FECAL OCCULT BLOOD TEST	Glucose
Fecal occult blood test (conducted at clinical site at check-in)	Ketones
	Microscopic examination
	pH
	Protein
PREGNANCY SCREEN** (females only)	Specific gravity
Urine pregnancy tests will be performed at screening and at discharge. Serum pregnancy test will be done at check-in on Day -1	
FSH and estradiol test will be done on post-menopausal females at screening and check-in on Day -1	OTHER TEST:
**the urine pregnancy tests may be performed in-clinic using CLIA-waived marketed kits.	Urine Random Creatinine test will be performed at screening, check-in, and discharge from the study
Saliva Alcohol Test (to be performed at screening and at check-in using CLIA -waived marketed kits)	VIRAL SCREEN*** (to be performed at screening only):
Urine Drug Screen (to be performed at screening and check-in using CLIA -waived marketed kits)	HBsAg
	HCV antibody test
	HIV antibody test

### 6.6.3 Experimental Safety Biomarker Assessment

Two aliquots of citrated plasma (1 ml each) for experimental safety biomarker assessments (e.g. D-Dimer, F1.2 tests) will be collected at pre-apixaban (within 1 hr. prior to dosing) on Day 1, and at 2.75 and 8 hrs. post-apixaban on Day 4. Experimental safety biomarker assessment will only be performed at the discretion of the Principal Investigator.

### 6.7 Electrocardiograms

A resting 12-lead electrocardiogram will be performed at screening, check-in, after administration of apixaban, and prior to discharge from the clinic site. Parameters assessed will include ventricular rate (bpm), PR interval (msec), QRS duration (msec), QT interval (msec) and QTc interval (msec). Additional ECGs may be performed at the discretion of the Principal Investigator.

### 6.8 Dispensing Study Drug

All study drugs will be prepared by the designated pharmacy personnel at [REDACTED]

#### 6.8.1 Ciraparantag

The study pharmacist or designated personnel will calculate the final volume of ciraparantag. Ciraparantag should be prepared on the day of dosing and stored at room temperature at least 1 hour before administration. The appropriate volume of Ciraparantag Injection will be withdrawn from the supplied vials.

Throughout this protocol, the active study drug doses are expressed as active drug substance (ciraparantag) (previously study drug doses were expressed as ciraparantag acetate with a content of 10 mg/mL). The administered dose is based on a concentration of 6 mg/mL ciraparantag and translates to the following dose conversions:

Ciraparantag Acetate	Ciraparantag	Dose Volume
600 mg	360 mg	60 mL
300 mg	180 mg	30 mL
100 mg	60 mg	10 mL
50 mg	30 mg	5 mL
25 mg	15 mg	2.5 mL

Ciraparantag will be prepared and administered by IV injection over a minimum of 10 minutes.

All ciraparantag doses must be labeled with the study number and date.

Study drug may be prepared on the day of dosing and will have an expiration of 4 hours at room temperature or will be refrigerated at 2-8°C (36-46°F) until use. All prepared solutions must be used within 24 hours. All unused drugs will be returned to the pharmacy. A record must be kept of all discarded solutions.

#### 6.8.2 Placebo

An equivalent volume of sterile 0.9% Sodium Chloride Injection, USP will be utilized as the placebo.

All placebo doses must be labeled with the study number and date.

Placebo may be prepared on the day of dosing and will have an expiration of 4 hours at room temperature or will be refrigerated at 2-8°C (36-46°F) until use. All prepared solutions must be used within 24 hours. A record must be kept of all discarded solutions.

#### 6.8.3 Apixaban

Apixaban will be dispensed as one tablet in a container labeled with the study number, subject number and date. All unused tablets will be returned to the pharmacy.

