### Summary of Main Changes Made in Version 1.0 to Generate Version 2.0

Item	Revision in Version 2.0

Dose Schema: In Synopsis and section 3.1
	
Dosing schema was revised. The version 2.0 dosing schema was replaced with following dosing schema.
  <pre> graph LR     A[Cohorts 1-3 Apixaban 10 mg BID for 3.5 days] --> B[Cohort 1 3 hours post Apixaban (Day 4): Ciraparantag 60 mg (100 mg ciraparantag acetate) or Placebo]     B --> C[Cohort 2 3 hours post Apixaban (Day 4): Ciraparantag 120 mg (200 mg ciraparantag acetate) or Placebo]     C --> D[Cohort 3 3 hours post Apixaban (Day 4): Ciraparantag 30 mg (50 mg ciraparantag acetate) or Placebo]   </pre>

Item	Revision in Version 2.0
Apixaban Dosage: 1. In Synopsis 2. In Study Procedure 3. In section 2 4. In section 3.1 5. In section 5.2.3 6. In section 5.3 7. In section 7.2.2 8. In section 7.2.3 9. In section 7.2.4.1	Increase apixaban dosage Increased apixaban dosage from 5 mg BID (Q12) for 3.5 days as a single oral tablet to 10 mg BID (Q12) for 3.5 days as two oral tablets
Exclusion Criteria #3	Clarify exclusion criteria Changed from “History of major bleeding, trauma, or surgical procedure of any type” to “History of major bleeding, trauma, or surgical procedure of any type based on PI discretion”
Stroke Assessment: In Synopsis	Add stroke assessment Add in Safety Assessments: “Stroke assessment”
Stroke Assessment In Study Procedures	Add stroke assessment Add stroke assessment in Study Procedure Table on Day 1 to 4 Add in k: “Stroke assessments will be performed by PI or designee at approximately 3 hours post-apixaban dose on the morning ( $\pm 1$ -hour window) on Day 1 to 4.”
Stroke Assessment In section 6.5	Add section 6.5 Stroke Assessment Add: “Stroke assessments will be performed by PI or designee at approximately 3 hours post-apixaban dose on the morning ( $\pm 1$ -hour window) on Day 1 to 4. PI or designee will check for stroke warning signs and physical symptoms: Stroke warning signs: 

• Sudden weakness or numbness of the face, arm or leg, especially on one side

• Sudden confusion or difficulty understanding

• Trouble speaking, walking or seeing

• Dizziness or loss of balance

• Sudden onset of severe headache

 Physical symptoms: 

• Facial smiling or showing of teeth on one side

• One arm does not move or drifts compared to the other on extension

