## 5 STUDY TREATMENT(S)

### 5.1 Description of Treatment(s)

The following dosage forms will be provided for this study:

- Ciraparantag for IV injection
- Placebo for IV injection
- Apixaban 5 mg tablets (commercial formulation Eliquis®, Pfizer/BMS) for oral administration

All doses of study drug (ciraparantag or placebo) will be administered by IV injection (over a minimum of 10 minutes) e.g. 60 mg ciraparantag (10 ml) will be administered at a rate of approximately 1 mL/min and 360 mg (60 ml) will be administered at a rate of approximately 6 mL/min into an indwelling catheter that is not attached to an IV solution and will not result in dilution of the study drug. The indwelling catheter will be flushed with 5.0 mL of sterile 0.9% Sodium Chloride Injection, USP before and after administration of study drug. All doses of study drug will be administered in a single-blinded-fashion.

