#### 5.2.3 Apixaban

All doses of apixaban (trade name Eliquis®; Pfizer/BMS) will be administered in an open-label manner. The ingestion of apixaban tablets will be witnessed by clinical site personnel.

Apixaban 10 mg administered twice daily Q12 as two 5 mg oral tablets for 3.5 consecutive days is a standard, FDA approved dose and is considered safe and well-tolerated in this population.

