## **5.8 Treatment Compliance**

All study drug will be administered by clinical site personnel by IV injection over a minimum of 10 minutes into an indwelling catheter that is not attached to an IV solution and will not result in dilution of the study drug. Following administration of the study drug, the indwelling catheter will be flushed with 5.0 mL of sterile 0.9% Sodium Chloride Injection, USP.

All doses of apixaban will be administered after meal with 240 ml of water under the supervision of clinical site personnel. The ingestion of all doses of apixaban will be witnessed by clinical site staff. A mouth and hand check of all subjects will be carried out to ensure that the tablets have been swallowed.

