#### 7.2.4 Day 4 Procedures

##### 7.2.4.1 Pre-study drug

The following activities and/or assessments will be performed on Day 4 before administration of study drug in all subjects:

- Administration of a single 10 mg dose of apixaban after breakfast; Maintain fast for 4 hours after the apixaban dosing; Water allowed ad libitum
- An ECG and vital signs
- Blood draw for PK assessment of apixaban and ciraparantag baseline at 2.75 hrs. post-apixaban
- Blood draw for WBCT measurement (triplicates post-apixaban at 2.75 hrs.)
- Blood draw for experimental safety biomarker assessment
- Randomization
- AEs and concomitant medications will be recorded
- Stroke assessment at approximately 3 hours post-apixaban dose on the morning ( $\pm 1$ -hour window)

##### 7.2.4.2 Study Drug Administration: Time 0

The following activities and/or assessments will be performed in the order listed on Day 4 in all subjects:

- Vital signs prior to study drug
- I.V. administration of study drug (ciraparantag or placebo)
- AEs and concomitant medications will be recorded

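### Does dispensing apixaban as one tablet per container conflict with a dose of two tablets?

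*Protocol*

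**What the plan says.** Apixaban appears in three kinds of text in the protocol.

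- **Supply.** Section 5.1 lists "Apixaban 5 mg tablets (commercial formulation" and gives the brand. Section 5.10.2 adds that they arrive in bottles of 60.
- **Dispensing.** Section 6.8 opens with "All study drugs will be prepared by the designated pharmacy personnel". Its subsection on apixaban, 6.8.3, reads "Apixaban will be dispensed as one tablet in a container labeled with the study number, subject number and date" and adds only that unused tablets go back to the pharmacy.
- **Dosing.** Section 5.2.3 has "Apixaban 10 mg administered twice daily Q12 as two 5 mg oral tablets for 3.5 consecutive days". Sections 7.2.2 and 7.2.3 repeat 10 mg twice daily for Days 1 to 3, and section 7.2.4.1 has "Administration of a single 10 mg dose of apixaban after breakfast" for Day 4. The SAP (sections 2.1, 2.2 and 3, and footnote k of its Table 1) gives the same 10 mg.

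The change summary for Version 2.0 records an increase from "5 mg BID (Q12) for 3.5 days as a single oral tablet to 10 mg BID (Q12) for 3.5 days as two oral tablets". It lists nine places where this was carried through. Part of the list runs "5. In section 5.2.3 6. In section 5.3 7. In section 7.2.2", so it passes from section 5.3 to section 7.2.2 without naming 6.8.3.

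Neither document gives a number of containers per administration.

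**The concern.** Section 6.8.3 is the protocol's only line on how the pharmacy dispenses apixaban, and it mentions one tablet where a dose needs two. The neighbouring subsections encourage a misreading: 6.8.1 and 6.8.2 require each ciraparantag or placebo dose to be labelled, so a reader may take the labelled apixaban container to be a dose as well.

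The change history points the same way. One tablet per container fits the superseded single-tablet regimen exactly, and 6.8.3 is absent from the list of places updated when the dose became two tablets. It is natural to suspect that the line was overlooked.

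If one container were handed out per administration, a subject would receive half the stated dose. The primary objective concerns reversal of anticoagulation under apixaban 10 mg twice daily at steady state, so systematic half-dosing would undermine what the trial sets out to study.

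**Working it through.** No sample size, error rate or estimator is involved. The check is a tablet count and a comparison of the sections.

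**Inputs**
- Tablet strength: 5 mg (protocol 5.1).
- Dose per administration: 10 mg, as two tablets (protocol 5.2.3).
- Schedule: twice daily on Days 1 to 3 and once on the morning of Day 4 (protocol 3.1).
- Tablets per container: 1 (protocol 6.8.3).

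**The plan's own figure**
- Tablets per administration = dose / strength = 10 mg / 5 mg = 2. This agrees with section 5.2.3.

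**Containers per administration**
- (tablets per administration) / (tablets per container) = 2 / 1 = 2.
- Both inputs are in the current text, and no other whole number satisfies both sections.

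**Totals per subject**
- Administrations = 3 × 2 + 1 = 7.
- As written: 7 × 2 = 14 tablets, or 70 mg.
- If one container were mistaken for one dose: 7 × 1 = 7 tablets, or 35 mg, at 5 mg each time. Staff could arrive there only by disregarding the two tablets in section 5.2.3 and the 10 mg in sections 7.2.2 to 7.2.4.1.

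**Does 6.8.3 equate a container with a dose?**
It does not say so. Its label carries study number, subject number and date, but no dose number or time. On a twice-daily day the present regimen gives 2 × 2 = 4 containers with the same listed label items. Single-tablet containers under the 5 mg regimen would have given 2 × 1 = 2. So this label would not have identified a particular dose under either regimen. That fits a single-tablet unit better than a dose pack.

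**What the change summary can show**
The nine places are the Synopsis, the Study Procedures table and sections 2, 3.1, 5.2.3, 5.3, 7.2.2, 7.2.3 and 7.2.4.1. Section 6.8.3 is not one of them. The summary is headed as covering main changes, so it need not be complete, and the Version 1.0 text of 6.8.3 is not available. Absence from the list is as consistent with a line that needed no edit, since a single-tablet container serves either regimen, as with an oversight. It is not evidence of an error.

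**What would catch a slip**
- Clinic staff witness ingestion (protocol 5.2.3).
- Section 5.8 adds "A mouth and hand check of all subjects will be carried out to ensure that the tablets have been swallowed", with tablets in the plural.
- Dosing deviations must be notified (protocol 10.9) and are listed by subject (SAP 4.2.2).
- Apixaban is assayed at 2.75 hours after the Day 4 dose (protocol 6.9.1).

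**The case for a change.** The strongest case for acting is that a dispensing instruction should need no inference. Read one way, with the container as the dose, 6.8.3 disagrees with 5.2.3; read the other way, the container count is missing. Four containers with the same listed label items would be prepared for each subject on each of Days 1 to 3, and nothing says which two belong to the morning dose. The safeguards are also less specific than they look. Section 5.12 on accountability speaks of test articles and study drug, and section 3.1 reserves the latter term for ciraparantag or placebo. The SAP listing of apixaban administration (4.8.1) names date and time but not tablet count. A one-line clarification would cost almost nothing.

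Parts of this stand. The container count is unstated, and the accountability section and the SAP listing cannot be relied on to show tablets per dose. For that reason neither is counted among the safeguards in the check.

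The rest does not carry the point. The reading that produces a conflict adds an equation of container and dose that 6.8.3 does not make, when another reading satisfies every section. The identical labels do no harm to the dose: all four containers hold the same open-label 5 mg tablet, so any two of them make up the administration. What is left is a number that follows from two stated numbers.

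**Conclusion.** No change to the plan follows. Sections 6.8.3 and 5.2.3 are compatible, and together they fix two single-tablet containers per administration. The gap is one unstated count, which pharmacy staff can fill in only one way if they follow the dosing sections. Carried out as written, the plan delivers the 10 mg stated in both documents at each of the seven administrations. Nothing in the documents indicates that any subject would be under-dosed, and design, sample size, the WBCT endpoint and the analyses are untouched.

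This rests on two assumptions: that staff read the dispensing line together with the dosing sections, and that 6.8.3 describes a packaging unit, which is all its wording says. The suggestion that the line was left over from Version 1.0 cannot be verified and has no bearing on the conclusion. A sponsor amending the protocol for other reasons might align the wording of 6.8.3 with 5.2.3 and 7.2.2 to 7.2.4.1, but that is an editorial choice. No view is taken here on the dose.

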### 6.9 Efficacy Assessments

Time 0 for all PK and PD assessments will be the end of the study drug injection. Where timing for assessments coincide, PD assessment(s) should be performed first, followed by PK assessment(s), and then ECGs, and vital signs will be performed. The tolerance window to complete PK and PD draws is as follow:

PK/PD Draw Tolerance Window

Sampling Time Point	Tolerance Window
Pre-dose	-60 minutes to 0 hour
>0 hour - 24 hour	-10 minutes to +10 minutes

Over the course of the study, the total estimated volume of blood to be sampled from each subject for the combined PK, PD and safety evaluations is approximately 175 mL.

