The pharmacodynamics results show that at pre-study drug on Day 3, mean observed WBCT after edoxaban dosing increased to similar levels in the placebo group and ciraparantag treatments. Over the one to six hours postdose interval (inclusive) after the first ciraparantag dose, complete reversal for WBCT was achieved in a higher percentage of subjects in the active treatments (82.9% for all doses) compared to the placebo group (60.0%). Across the 30 mg ciraparantag to 360 mg PER977 treatments, the rate of complete reversal at 30 mg was slightly lower (62.5%) while the rate was similar for 60 mg or higher dose levels (88.9% to 100%). Both evaluable subjects (100%) in the 15 mg PER977 treatment had partial reversal. None of the subjects in any of the placebo or active treatments had percent-of-baseline WBCT >190% at any time point (i.e., no reversal).

Results of statistical comparisons showed ciraparantag had no impact on re-anticoagulation with edoxaban as measured by WBCT at pre-study drug on Day 4 versus pre-study drug on Day 3. Over the 1 to 6 hour postdose interval (inclusive) after the second ciraparantag dose on Day 4, the rates of complete reversal were comparable to Day 3. Overall, 88.6% of the subjects in the active ciraparantag treatments and 53.3% of subjects in the placebo group had complete reversal. Across the 30 mg to 360 mg active treatments, the rate of complete reversal was slightly lower (66.7%) for 180 mg while the rate was similar for all other dose levels (87.5% to 100%). None of the subjects in any of the placebo or active treatments had percent-of-baseline WBCT >190% at any time point (i.e., no reversal).

Treatment comparisons of percent-of-baseline WBCT showed lower values compared to placebo following 60 mg to 360 mg ciraparantag on Day 3 that were statistically significant at most time points between five minutes to three hours after the end of injection (geometric least-squares [LS] ratios ranged from 86.52% to 93.70%); and following 30 mg to 360 mg ciraparantag on Day 4 at most time points between five minutes to six hours after the end of injection (geometric LS ratios ranged from 84.91% to 95.71%). On both study days, WBCT at different dose levels in the active ciraparantag treatments returned to baseline within the 0.083-hour to 0.75-hour time points. Post-baseline WBCT in placebo-treated subjects did not decrease to baseline level until the 1-hour (Day 4) to 1.5-hour (Day 3) post-study drug time point.

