**6.9.2 Pharmacodynamic Assessment**

Blood samples (2 ml) for measuring of clotting time by WBCT will be collected at the following time points:

Day 1: pre-apixaban baseline (within 1 hr. prior to dosing)

Day 4: post-apixaban at 2.75 hr and post-study drug at 15, 30, 45 minutes, and 1, 3, 5, 24 hrs. (only subjects with at least 20% increase of clotting time from the Day 1 pre-apixaban baseline will be randomized).

TriPLICATE WBCT will be done Day 1 pre-apixaban baseline, post-apixaban at 2.75 hrs. and post-study drug at 1 hr on Day 4.

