3.4 Sample Size Justification

The study population will consist of healthy male and female adults, age 50-75 years (inclusive). No formal sample size calculations were performed for this study; sixteen

(16) subjects enrolled in each For cohort (3:1; active: placebo) is considered an adequate number of subjects to achieve the objectives of the study.

Estimated number of subjects screened: 120

Planned number of subjects randomized: 48

Planned number of evaluable subjects: 48

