- Statistically significant complete reversal, relative to mean placebo WBCT, is defined as $p < 0.05$, (one tailed) from the comparison of means between treatment and placebo at 15, 30, 45 minutes or 1 hour post study drug administration as measured by one-way Analysis of Variance (ANOVA) at study completion. Distribution diagnostics will be performed to assure assumptions associated with using ANOVA are met. The one-tailed Dunnett's test will be used for comparisons of treatment means.

Analysis of Means (ANOM) methods will also be used to compare means and variances across groups. These methods will be appropriate to test if any of the group means are statistically different from the overall mean or if the group standard deviations are statistically different from the root mean square error (RMSE).

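### The ±10-minute draw tolerance makes the first-hour sampling windows overlap, adding avoidable timing noise to the primary WBCT comparison and to observed Cmax

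*Protocol*

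**What the plan says.** The tolerance table in Protocol section 6.9 has one row for all post-dose PK and PD draws up to 24 hours, and its entry runs from minus "10 minutes to +10 minutes". The clock is defined in the same section: "Time 0 for all PK and PD assessments will be the end of the study drug injection". The WBCT schedule is in Protocol section 6.9.2: "Day 4: post-apixaban at 2.75 hr and post-study drug at 15, 30, 45 minutes, and 1, 3, 5, 24 hrs". PK samples after study drug follow the same times.

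SAP section 4.7.1 defines statistically significant complete reversal by a one-sided p below 0.05 from the "comparison of means between treatment and placebo at 15, 30, 45 minutes or 1 hour post study drug administration", using one-way ANOVA. It adds: "The one-tailed Dunnett's test will be used for comparisons of treatment means". That section summarises WBCT values at scheduled time points. It lists collection times and their deviations, but gives no rule for using them in the comparison.

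Actual times do enter elsewhere: the derived PD parameters (SAP section 4.7.2) and the noncompartmental PK calculations (SAP section 4.6.2). Cmax, however, is read straight from the observed concentrations (SAP Table 2). It then goes into the dose-proportionality model and the adjacent-dose comparison (SAP section 4.6.3).

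**The concern.** A fixed tolerance of 10 minutes is trivial at 24 hours but is two-thirds of the nominal time at 15 minutes, and it exceeds half of the 15-minute spacing in the first hour. The protocol already widens its windows with time for vital signs (section 6.4: 10, then 20, then 30 minutes). It does not do so for the endpoint that the trial is built on.

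Two results are exposed. First, the primary between-group comparison treats a value drawn anywhere between 5 and 25 minutes as a 15-minute value, and so on up the hour. Any change in WBCT within those 20 minutes becomes within-group scatter, in groups of about 12. Second, ciraparantag is cleared within minutes, so the highest observed concentration depends heavily on when the first sample happened to be taken. Using the actual time in the other PK calculations does not change the value recorded as Cmax.

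**Working it through.** The plan states no power, SD or timing distribution that bears on this point, so there is no figure of its own to reproduce.

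**1. Windows.** Inputs: nominal times 15, 30, 45 and 60 minutes and tolerance ±10 (Protocol sections 6.9 and 6.9.2). Overlap = upper limit of one window minus lower limit of the next.

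| Tolerance | 15 min | 30 min | 45 min | 60 min | Overlap per pair |
|---|---|---|---|---|---|
| ±10 | 5–25 | 20–40 | 35–55 | 50–70 | 5 min |
| ±7.5 | 7.5–22.5 | 22.5–37.5 | 37.5–52.5 | 52.5–67.5 | 0 (they touch) |
| ±5 | 10–20 | 25–35 | 40–50 | 55–65 | none (5-min gap) |

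At ±10 the overlaps cover 3 × 5 = 15 of the 65 minutes spanned (23%). The windows at 3, 5 and 24 hours do not overlap with anything.

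**2. Spacing.** The actual gap between two draws planned 15 minutes apart can be 15 − 20 = −5 to 15 + 20 = 35 minutes. If both errors were independent and uniform over ±10 (an assumption), the order would reverse with probability (20 − 15)² / (2 × 20²) = 25/800, about 3%. At ±5 the gap is 5 to 25 minutes and the order cannot reverse.

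**3. Observed Cmax.** Input: mean half-life 12.4 to 20.2 minutes in the repeat-dose edoxaban study (Protocol section 1.2.4). That study typically found Cmax at its first post-dose sample. Assume log-linear decline after the injection ends. The fold change over a span of s minutes is 2^(s / half-life).

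- ±10, span 5–25, s = 20: 2^(20/12.4) = 3.06 and 2^(20/20.2) = 1.99.
- ±5, span 10–20, s = 10: 2^(10/12.4) = 1.75 and 2^(10/20.2) = 1.41.

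If draw times were spread uniformly over the window (again an assumption), their SD would be 20/√12 = 5.77 minutes. The SD that this adds to log Cmax is 5.77 × ln 2 / half-life, which is 0.32 to 0.20. At ±5 it halves, to 0.16 to 0.10. The documents give no between-subject SD for Cmax, so the effect on the 90% interval for the slope cannot be worked out.

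**4. WBCT, illustration only.** Assume that the treatment–placebo contrast follows (1 − exp(−t/a)) × exp(−t/b), with a from 3 to 20 minutes and b from 60 minutes to no offset, and that draws are uniform over ±10. Then:

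- the mean contrast at 15 minutes falls by about 2–6%, and at 30 to 60 minutes it changes by less than 2%;
- timing scatter is at most about 27% of the contrast at 15 minutes and at most about 10% at 30 to 60 minutes;
- for 12 against 12 in a plain one-sided test at 0.05, with an assumed contrast of 10–20 points and SD of 8–15, power falls by 1.5 points or less when scatter is 20% of the contrast and by about 3 points when it is 30%.

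The 12 per group comes from the design: 16 × 3/4 = 12 active per cohort, and 3 × 4 = 12 pooled placebo.

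**The case against.** The strongest reply is that little follows from the overlap itself. Each sample keeps its scheduled label and nothing in the SAP re-bins samples by window, so a 22-minute draw that fits two windows is still analysed once, as what it was planned to be. Both arms share the same tolerance and the WBCT staff are blinded. Ten minutes is a limit, not the expected error, in confined subjects. Actual times are used for the derived PD parameters, timing deviations are listed, and deviations that could affect WBCT bear on the PD population. All of this stands, and it limits the PD effect to noise, probably small and mainly at 15 minutes.

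A reader might infer something stronger: that the first hour is the only period in which the arms are expected to differ. The nearest support is that placebo WBCT in the repeat-dose edoxaban study "did not decrease to baseline level until the 1-hour (Day 4) to 1.5-hour (Day 3) post-study drug time point". The same section, however, reports significant differences at most time points up to 3 hours on one day and 6 hours on the other. Protocol section 1.2.1 reports reversal versus placebo for 24 hours, and section 1.2.3 reports a clear separation over 1 to 6 hours after enoxaparin. This plan itself defines sustained reversal over 1 to 5 hours. None of those studies used apixaban, so the time course of placebo recovery here is not known in advance.

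Two other inferences also fail. The half-life figures describe drug concentration and cannot be carried over to WBCT, since reversal was reported to last far longer than the drug does. A 70-minute value can count as reversal by 1 hour, but it can do so in either arm, so no direction of bias is shown.

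**Conclusion.** The point holds as a minor, inexpensive improvement. The overlap of 5 minutes per adjacent first-hour pair is a matter of arithmetic. The four affected times are those of the primary comparison, which is specified by scheduled time with no analysis on actual time.

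For WBCT the consequence is extra noise of a size that the documents do not allow one to derive; the small power losses above rest on assumed curves, SDs and timing errors. For observed Cmax the consequence is better grounded: a permitted 3.1- to 2.0-fold range in the first sample, given the stated half-life and log-linear decline, which ±5 minutes would cut to 1.75- to 1.41-fold. The documents support neither a claim of bias between arms nor a claim that the treatment effect is confined to the first hour.

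**What to change.** In the tolerance table of Protocol section 6.9, split the post-dose row: ±5 minutes for the 15, 30, 45 and 60 minute draws, and ±10 minutes from 3 hours on. Any value up to ±7.5 minutes removes the overlap; ±5 also halves the permitted span for Cmax.

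If sampling is already complete, add one sensitivity analysis to SAP section 4.7.1 that repeats the primary comparison either on actual times or without first-hour draws more than 5 minutes off nominal. This will not repair Cmax, so report the actual first-draw times beside the Cmax results. An analysis on actual times also needs one time origin. Protocol section 9.9 counts PD parameter times from the start of the injection, while Protocol section 6.9 and SAP section 4.7.2 count from its end. With an injection of at least 10 minutes, that difference is at least as large as the present tolerance, and the sections must be reconciled.

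The cost is tighter timing for site staff, who take WBCT and two PK samples at each point, and a few more recorded deviations. It looks workable: subjects are in-patients with an indwelling catheter, and the earlier studies described in Protocol sections 1.2.3 and 1.2.4 measured at 2 and 5 minutes after the injection.
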